				Equal Scores at both time points	
Upper GI	NIH Upper GI Score 0 after previous involvement	Decrease in NIH Upper GI Score by 1 or more points	Increase in NIH Upper GI Score by 1 or more points, except 0 to 1	Score = 0	Score = 0 or 1
				Equal Scores at both time points	
Lower GI				Score = 0	Score = 0 or 1

Organ	Complete response ¹ NIH Lower GI Score 0 after previous involvement	Partial response ¹ Decrease in NIH Lower GI Score by 1 or more points	Progression ¹ Increase in NIH Lower GI Score by 1 or more points, except from 0 to 1	No involvement/unchanged	
				Baseline	Post-baseline
				Equal Scores at both time points	
Liver	Normal ALT, alkaline phosphatase, and Total bilirubin after previous elevation of 1 or more	Decrease by 50%	Increase by 2 x ULN	See text	
Lungs ²	Normal %FEV1 after previous involvement If PFTs not available, NIH Lung Symptom Score 0 after previous involvement	Increase by 10% predicted absolute value of %FEV1 If PFTs not available, decrease in NIH Lung Symptom Score by 1 or more points	Decrease by 10% predicted absolute value of %FEV1 If PFTs not available, increase in NIH Lung Symptom Score by 1 or more points, except 0 to 1	Change of %FEV1 from baseline < 10% (see text for additional rules) If PFTs not available, Score = 0 Score = 0 or 1	
Joint and fascia	Both NIH Joint and Fascia Score 0 and P-ROM score 25 after previous involvement by at least 1 measure	Decrease in NIH Joint and Fascia Score by 1 or more points or increase in P-ROM score by 1 point for any site	Increase in NIH Joint and Fascia Score by 1 or more points or decrease in P-ROM score by 1 point for any site	J&F Score=0 and P-ROM Score=25	J&F Score=0 and P-ROM Score=25 Any situation that does not qualify for response or progression (see text)

¹ response definition as per Table 4 in the published NIH criteria, see [Lee et al 2015](#), ULN indicates upper limit of normal.

² Lung response assessment is determined based on an improvement (e.g. 50% to 60%) or worsening (e.g. 50% to 40%) in %FEV1 of 10% or more predicted absolute value.

Figure 16-1 Criteria to determine liver response: general rules

at baseline visit				at each post-baseline visit		
Observed data	Liver involvement: Any parameter > ULN?	ULN	Calculate UL2= 2 x ULN	- Document observed values for ALT, AP and BIL and compare to baseline values to determine the liver response		
				Observed data	Action	Liver response
				ALT_value AP_value BIL_value		

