				IF values of ALL 3 parameters are normal (i.e. < ULN)	Assess response	CR (if liver involvement at baseline) Unchanged/no involvement (if NO liver involvement at baseline)
				IF the value of at least one parameter is elevated (i.e. > ULN)	Calculate & check change from baseline	
				In case of improvement: Percent decrease from baseline by at least 50%? Percent change = $100 \times (\text{ALT_value} - \text{ALT_baseline}) / \text{ALT_baseline}$ Repeat for AP and BIL		PR (if at least one of the 3 values shows > 50% decrease from baseline) Unchanged/no involvement (if NO value decreased > 50%, improvement less than 50% does not qualify for PR)
				In case of worsening: Check increase of observed absolute value from baseline: Is increase more than 2 x ULN? ALT_value > (ALT_baseline + UL2_ALT)? AP_value > (AP_baseline + UL2_AP)? BIL_value > (BIL_baseline + UL2_BIL)?		Progression (if at least one of the 3 values shows increase by > 2 x ULN from baseline) Unchanged/no involvement (if NO value increased by 2 x ULN, worsening too low for PD)
ALT_baseline	YES or NO?	ULN_ALT	UL2_ALT			
AP_baseline		ULN_AP	UL2_AP			
BIL_baseline		ULN_BIL	UL2_BIL			

Figure 16-2 Criteria to determine liver response: Example 1 (PR)

at baseline visit
 
 - Document observed baseline values (last data obtained before randomization) for ALT, Alkaline phosphatase (AP) and total bilirubin (BILI) - Document the corresponding upper normal limit (ULN) for each parameter and calculate the corresponding value = 2 x ULN 				
at each post-baseline visit
 
 - Document observed values for ALT, AP and BILI and compare to baseline values to determine the liver response 		

Observed data
 
ALT= 40 AP= 250 BILI= 19.8
				
Observed data
 
ALT= 34 AP= 110 BILI= 18.0
	
Action
 
Assess response
	
Liver response
 
CR (if liver involvement at baseline)
 
Unchanged/no involvement (if NO liver involvement at baseline)

Liver involvement: Any parameter > ULN?
 
YES (ALT and AP)
				
IF the value of at least one parameter is elevated (i.e. > ULN)
	
Action
 
Calculate & check change from baseline
	
ALT= 40	35 U/L	2 x 35 = 70	
In case of improvement:
 
Percent decrease from baseline by at least 50%?
 
ALT : $100 \times (34 - 40) / 40 = - 15\%$ AP : $100 \times (110 - 250) / 250 = - 56\%$ BILI: $100 \times (18.0 - 19.8) / 19.8 = - 9\%$
			

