16.4.2.3 Joints and fascia

NIH Joint and Fascia score as well as photographic range of motion (P-ROM) score are evaluated.

Involvement at baseline is defined as NIH Joint and Fascia score ≥ 1

A decrease (i.e. worsening) of any site in P-ROM is considered as progression (irrespective of the change in the NIH Joints and Fascia score). Similarly, an increase (worsening) in the NIH Joints and Fascia score is considered as progression (irrespective of the change in any of the 4 P-ROMs)

Accordingly, a partial response is only possible if:

- at least one site in P-ROM increased by 1 or more points
- and all other sites remain unchanged compared to baseline
- and NIH Joints and Fascia score is equal to or decreased from baseline

OR

- Decrease of the NIH Joints and Fascia Score from baseline with NO worsening in P-ROM for any site

Example for progression

[figure not shown]
	Baseline	Post-baseline	
NIH Joints and Fascia Score	1	1	equal
P-ROM			
Shoulder	6	6	equal
Elbow	6	5	decrease
Wrist/finger	6	6	equal
Ankle	3	4	increase
TOTAL	21	21	

Example for partial response

	Baseline	Post-baseline	
NIH Score	1	1	equal
P-ROM			
Shoulder	6	6	equal
Elbow	6	6	equal
Wrist/finger	6	6	equal
Ankle	3	4	increase
TOTAL	21	22	

Photographic Range of Motion (P-ROM)

Figure 16-4 Photographic Range of Motion (P-ROm)

Source: [Lee et al 2015](#)

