16.4.2.4 Skin

The skin score is based on the Body Surface Area (BSA) and the involvement of sclerotic features. [Table 16-4](#) lists the criteria to be applied to assess the skin score at baseline and at each post-baseline visit. Response assessment is to be performed according to the criteria defined in [Table 16-3](#).

Table 16-4 Assessment of the skin score based on BSA and sclerotic features

Total BSA involved (%)	Score %BSA	Sclerotic involvement?	Type of sclerotic involvement	Skin feature score	Skin Score ¹
none	0	no	NA	0	0
1% to 18%	1	no	NA	0	1
1% to 18%	1	yes	Superficial only (able to pinch)	2	2
1% to 18%	1	yes	Unable to pinch ("Hidebound") Deep sclerotic features Impaired mobility Ulceration	3	3
19% to 50%	2	No	NA	0	2

Total BSA involved (%)	Score %BSA	Sclerotic involvement?	Type of sclerotic involvement	Skin feature score	Skin Score ¹
19% to 50%	2	yes	Superficial only (able to pinch)	2	2
19% to 50%	2	yes	Unable to pinch ("Hidebound") Deep sclerotic features Impaired mobility Ulceration	3	3
More than 50%	3	no	NA	0	3
More than 50%	3	yes	Superficial only (able to pinch)	2	3
More than 50%	3	yes	Unable to pinch ("Hidebound") Deep sclerotic features Impaired mobility Ulceration	3	3

¹ Overall skin score to be used for the response assessment taken as worst of Score for %BSA and Skin feature score
NA = not applicable

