16.4.3 Efficacy Assessments - Overall response assessment at one time point

Following the NIH working group recommendations the overall response evaluation (at each scheduled post-baseline time point/assessment) will be based on the evaluations for skin, eyes, mouth, esophagus, upper GI, lower GI, liver, lungs and joints/fascia. For each post-baseline assessment comparison will be made to baseline (C1D1).

- Complete response is defined as complete resolution of all signs and symptoms of cGvHD in all evaluable organs without addition of new systemic therapy, including CNIs.
- Partial response is defined as an improvement in at least one organ (e.g. improvement of 1 or more points on a 4 to 7 point scale, or an improvement of 2 or more points on a 10 to 12 point scale) without progression in other organs or sites, or initiation/addition of new systemic therapies.
- Lack of response is defined as unchanged, mixed response, or progression.
- Progression is defined as worsening of at least one organ and no improvement (CR or PR) in any other organ.
- Mixed response is a CR or PR in at least 1 organ accompanied by progression in another organ.
- Unchanged response is defined as stable disease or absence of improvement in any organ involved by cGvHD.

cGvHD Flare: is defined as any increase in symptoms or therapy for cGvHD after an initial response (CR or PR). A cGvHD flare is not considered a treatment failure unless a change of therapy or addition of another systemic treatment, including CNIs, occurs.

cGvHD Recurrence is defined as the return of cGvHD disease after tapering off study treatment due to response. Following completion of a taper of systemic therapy, if worsening of cGvHD symptoms occur, the patient is allowed to resume treatment for cGvHD as per local institutional practice. For the statistical analyses re-start of treatment for cGvHD is handled in the same way as addition or initiation of new systemic treatment.

Table 16-5 summarizes the rules for overall response assessment based on organ-specific evaluations at a scheduled post-baseline visit (e.g. the primary endpoint at Month 6 – Cycle 7 Day 1).

Table 16-5 Overall response evaluation

	Organ-specific response ¹				

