Skin	CR / not involved	PR or CR in at least one organ with baseline involvement AND no progression in any other organ (i.e. CR, PR, unchanged, no involvement), assuming overall CR has not been achieved	PR or CR in one or more organ(s) with baseline involvement AND progression in one or more organs (incl. new occurrence in an organ with no baseline involvement)	Progression in one or more organ(s) with baseline involvement OR new occurrence in an organ with no baseline involvement AND no CR or PR in any other organ	Organ-specific response 'unchanged' for all organs (incl. no involvement)
Eyes	CR / not involved				
Mouth	CR / not involved				
Esophagus	CR / not involved				
Upper GI	CR / not involved				
Lower GI	CR / not involved				
Liver	CR / not involved				
Lungs	CR / not involved				
Joints and fascia	CR / not involved				
Overall response	CR	PR	Mixed response	Progression	Unchanged response

¹ at least one organ must be involved at baseline. Organ-specific response versus baseline status.

Source: Lee S, Wolff D, Kitko C, et al. Measuring therapeutic response in chronic graft-versus-host disease. National institutes of health consensus development project on criteria for clinical trials in chronic graft-versus-host disease: IV. The 2014 response criteria working group report. Biol Blood Marrow Transplant. 2015;984-999

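### Does the liver rule in Figure 16-1 need a tie-break for a visit that meets both partial response and progression?

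*Protocol*

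**What the plan says.** Protocol 16.4.2.1 and Figure 16-1 compare ALT, AP and bilirubin with their baseline values. The improvement branch ends in "PR (if at least one of the 3 values shows > 50% decrease from baseline"), and the worsening branch in "Progression (if at least one of the 3 values shows increase by > 2 x ULN from baseline"). Neither says which prevails if different values meet each branch at one visit, and the two worked examples do not cover it. The improvement branch first asks for "Percent decrease from baseline by at least 50" per cent, whereas its result needs more than 50%. The liver row of Table 16-3 has "Decrease by 50" per cent, as in the NIH table reproduced in Appendix 16.3.

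The other multi-component organs do have a rule. For joints and fascia, "A decrease (i.e. worsening) of any site in P-ROM is considered as progression". The skin score is "taken as worst of Score for %BSA and Skin feature score".

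Across organs, section 16.4.3 states: "Mixed response is a CR or PR in at least 1 organ accompanied by progression in another organ". The partial-response column of Table 16-5 requires "PR or CR in at least one organ with baseline involvement AND no progression in any other organ".

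SAP 2.5.1 uses overall response as recorded on the CRF. SAP 2.5.4 adds an organ-by-organ description and a sensitivity analysis that drops assessments departing from the protocol criteria (deviation OTH14).

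**The concern.** If the liver was involved at baseline, no other organ has progressed and no new systemic therapy was started, a liver that meets both branches decides overall response by its label alone. Labelled partial response, the subject is a responder. Labelled progression, the overall result is mixed response or progression, and both are non-response. Table 16-5 does not settle it: its partial-response column looks for progression in some other organ, while its mixed-response column is met by progression in any organ. Two assessors could therefore classify the same results differently without breaching the protocol. The OTH14 exclusion would keep both, and no planned analysis re-derives the liver label. ORR at Cycle 7 Day 1 and Cycle 4 Day 1, best overall response and duration of response all depend on it.

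Two smaller points were attached. A value that was normal at baseline can earn partial response by halving while the raised values stay put. And the partial-response threshold is worded in two ways.

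**Working it through.** **1. The plan's own figures.** With exact two-sided 90% limits, 27/42 gives 0.505 to 0.765, and the probability of at least 27 responders at a true ORR of 70% is 0.836. For 46 subjects, 30/46 gives 0.521 to 0.768, with probability 0.809. Both match Table 12-1. Coding Figure 16-1 also reproduces its two worked examples (partial response in Figure 16-2, unchanged in Figure 16-3).

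**2. Can one visit meet both branches?** Yes. Figure 16-3 has baseline ALT 34, AP 160, bilirubin 19.8 and ULN 35, 92, 20.5. If AP goes to 70, the change is 100 x (70 - 160)/160 = -56.3%, which is partial response. If ALT goes to 110 at the same visit, it exceeds 34 + 2 x 35 = 104, which is progression.

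**3. How often?** The documents give no frequency, so this rests on assumptions: lognormal values, no true change, within-subject CV 20% to 30%. Put s = sqrt(ln(1 + CV^2)); the log ratio of post-baseline to baseline has SD sqrt(2) x s. At CV 30%, s = 0.294 and the SD is 0.415. The chance that any one of the three values falls by more than 50% while any one rises by more than 2 x ULN was simulated; the last digit carries simulation error.

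| Baseline pattern | CV 20% | CV 25% | CV 30% | CV 30%, falling value raised at baseline | CV 30%, correlation 0.5 |
|---|---|---|---|---|---|
| Figure 16-3 | 0.004% | 0.07% | 0.36% | 0.03% | 0.005% |
| Figure 16-2 | 0.03% | 0.28% | 0.95% | 0.50% | 0.03% |
| All three at 3 x ULN | 0.13% | 0.95% | 2.86% | 2.86% | 0.13% |

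The first three columns of percentages assume independent values. Suppose half of the 46 enrolled subjects (23) have liver involvement, the top of an assumed range of 10% to 50%. Expected conflicts at one visit, CV 30%:
- independent: 23 x 0.0036 = 0.08; 23 x 0.0095 = 0.22; 23 x 0.0286 = 0.66;
- correlation 0.5: 23 x 0.00005 = 0.001; 23 x 0.0003 = 0.007; 23 x 0.0013 = 0.03.

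The 0.66 comes from a baseline pattern that neither protocol example resembles. These are conflicts, not changed responders: the conditions on other organs and on new therapy reduce them further.

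**4. Partial response from a normal value.** At CV 30%, one value halves by chance with probability Phi(ln 0.5/0.415) = 0.0475; at least one of two normal values does so with probability 1 - (1 - 0.0475)^2 = 0.0927. At the assumed 70% ORR, 46 x 0.30 = 13.8 subjects are non-responders. If 4 of them hang on the liver alone, 4 x 0.0927 = 0.37 extra responders are expected. With 1 such subject and CV 20%, the figure is 0.01. If no liver value was raised at baseline, Table 16-5 stops the liver from producing an overall partial response.

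**5. Threshold wording.** AP 250 to 125 is exactly -50.0% and still above ULN: partial response under one wording, unchanged under the other. Any other fall gives the same answer.

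**6. Weight of one subject.** 1/46 = 2.2 points. The 90% interval at 30/46 is 0.768 - 0.521 = 0.247 wide. At 29/46 the lower limit is 0.499, so one subject matters to the 50% mark only at 29 or 30 responders; at a true ORR of 70% that has probability 0.073 + 0.096 = 0.169.

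**The case for a change.** The best argument for acting is that noise is the wrong model. Under treatment, ALT may truly fall while AP truly rises, and then conflicts could exceed the table. If 1% or 2% of all 46 subjects counted as responders under one reading only, the probability of a lower limit of at least 50% would drop from 0.809 to 0.765 or 0.717. A clarification would also be cheap: laboratory results and reference ranges are already in the eCRF, and the final report still covers duration of response and best overall response to study end.

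Part of this stands. The frequency is unknown, and a precedence sentence would have been good drafting at the outset. But if 5% of 23 liver-involved subjects were in conflict, that is 1.15 subjects, or 1.15/46 = 2.5 points, about a tenth of the interval's width. The SAP tests no hypothesis, so crossing 50% is not a formal failure.

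A re-derivation would be post hoc for Cycle 7 Day 1 and Cycle 4 Day 1, whose analyses belong to the interim report and are not to be repeated, and the recorded response would remain primary in any case. For duration of response, liver progression alongside another organ in response is mixed response, so the liver label sets a progression date only when no other organ is in response. The organ-specific table and the full laboratory listings let a reader trace any such subject.

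Requiring the falling value to be raised at baseline would be a trade-off, not a correction. It is narrower than the NIH criterion that defines the endpoint and would cost comparability with trials using that criterion unfiltered.

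**Conclusion.** The observation is correct, but no change to the plan follows. Figure 16-1 leaves a within-liver conflict undecided. An assessor has an evident model to borrow, since joints and fascia and skin both let the worse finding prevail. On the stated assumptions (CV up to 30%, at most 23 liver-involved subjects, no true change), the expected number of conflicts is below one subject: 0.08 to 0.66 with independent values and 0.001 to 0.03 with correlation 0.5, before the further conditions needed to reach ORR. Larger true changes could raise these figures, but each affected subject moves ORR by only 2.2 points in an estimate with a 90% interval about 25 points wide. Partial response from a normal value follows the NIH rule and adds fewer than 0.4 expected responders. The threshold discrepancy is a clerical slip that matters only at exactly 50%.

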16.4.2.2 Lung

- Response assessment for Lung will be based on %FEV1: The %FEV1 value should be prioritized for response assessment. However, if the pulmonary function tests are not available or reliable, for example in young children or in sick children, the lung symptom score may be used for the response assessment. Refer to Table 16-3. A patient with baseline value %FEV1 $\geq 75\%$ is considered as having no lung involvement.
- A post-baseline value of %FEV1 > 80% is defined as ‘Complete Response’ if the baseline value was %FEV < 75%, irrespective of the percent increase.
- Partial response: Increase of absolute value of %FEV1 of 10% (e.g. 50% to 60%) or more from baseline (only if %FEV1 < 70% at baseline) and not CR.
- Progression: Absolute value of %FEV1 < 65% and decrease of 10% (e.g. 50% to 40%) or more from baseline.
- Unchanged: any situation not covered by the three bullet points above.

Handling of missing data:

- If baseline %FEV1 is missing and the post-baseline %FEV1 $\geq 75\%$ the lung response for that post-baseline visit is to be assigned to ‘unchanged/no involvement’.

If baseline %FEV1 is missing and Lung Score = 0 at baseline and the post-baseline %FEV1 < 65% the lung response for that post-baseline visit should be assigned a ‘progression’.

16.4.2.3 Joints and fascia

NIH Joint and Fascia score as well as photographic range of motion (P-ROM) score are evaluated.

Involvement at baseline is defined as NIH Joint and Fascia score ≥ 1

A decrease (i.e. worsening) of any site in P-ROM is considered as progression (irrespective of the change in the NIH Joints and Fascia score). Similarly, an increase (worsening) in the NIH Joints and Fascia score is considered as progression (irrespective of the change in any of the 4 P-ROMs)

Accordingly, a partial response is only possible if:

- at least one site in P-ROM increased by 1 or more points
- and all other sites remain unchanged compared to baseline
- and NIH Joints and Fascia score is equal to or decreased from baseline

OR

- Decrease of the NIH Joints and Fascia Score from baseline with NO worsening in P-ROM for any site

Example for progression

[figure not shown]
	Baseline	Post-baseline	
NIH Joints and Fascia Score	1	1	equal
P-ROM			
Shoulder	6	6	equal
Elbow	6	5	decrease
Wrist/finger	6	6	equal
Ankle	3	4	increase
TOTAL	21	21	

Example for partial response

	Baseline	Post-baseline	
NIH Score	1	1	equal
P-ROM			
Shoulder	6	6	equal
Elbow	6	6	equal
Wrist/finger	6	6	equal
Ankle	3	4	increase
TOTAL	21	22	

Photographic Range of Motion (P-ROM)

Figure 16-4 Photographic Range of Motion (P-ROm)

Source: [Lee et al 2015](#)

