2.5.1 Primary endpoint

The primary efficacy variable of the study is **overall response rate (ORR)** at Cycle 7 Day 1, defined as the proportion of subjects demonstrating a complete response (CR) or partial response (PR), according to the NIH Consensus Criteria ([Lee et al 2015](#)) as reported in the CRF. Note that response is relative to the assessment of cGvHD at baseline.

- **Complete response** is defined as complete resolution of all signs and symptoms of cGvHD in all evaluable organs without initiation of any new systemic therapy.
- **Partial response** is defined as an improvement in at least one organ (e.g. improvement of 1 or more points on a 4 to 7 point scale, or an improvement of 2 or more points on a 10 to 12 point scale) without progression in other organs or sites, or initiation/ addition of new systemic therapies.
- **Lack of response** is defined as unchanged, mixed response, or progression. (Please refer to Table 8-3 and Table 16-3 in the protocol for the definitions of "unchanged", "mixed response" and "progression".)

cGvHD Flare and **cGvHD Recurrence** are not considered as a treatment failure, unless they require a change or addition of another systemic treatment defined as below.

- **cGvHD Flare** is defined as any increase in symptoms or therapy for cGvHD after an initial response (CR or PR). A cGvHD flare is not considered a treatment failure unless a change or addition of another systemic treatment, including CNIs, occurs.
- **cGvHD Recurrence** is defined as the return of cGvHD disease after tapering off study treatment due to response. Following completion of a taper of systemic therapy, if worsening of cGvHD symptoms occur, the patient is allowed to resume treatment for cGvHD as per local institutional practice. For the statistical analyses, re-start of treatment for cGvHD is handled in the same way as addition or initiation of new systemic treatment.

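### Protocol 16.4.2.3 and Table 16-3 define baseline joint/fascia involvement differently, so a child with joint score 0 and P-ROM below 25 has no single CR/PR classification and, on one reading, no settled responder status

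*Protocol*

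**What the plan says.** - **Protocol 16.4.2.3 (text).** "Involvement at baseline is defined as NIH Joint and Fascia score" of 1 or more. The P-ROM score is not mentioned in that sentence. The partial-response bullets below it accept "at least one site in P-ROM increased by 1 or more points", provided the other sites are unchanged and the joint score is not worse. They do not require baseline involvement.
- **Protocol Table 16-3, joint and fascia row (printed within 16.4.2.1).** CR is "Both NIH Joint and Fascia Score 0 and P-ROM score 25 after previous involvement by at least 1 measure". PR is "Decrease in NIH Joint and Fascia Score by 1 or more points or increase in P-ROM score by 1 point for any site". The baseline state for no involvement is "J&F Score=0 and P-ROM Score=25". Table 4 of the NIH criteria, reproduced in Appendix 3 (Section 16.3), words CR in the same way.
- **Protocol Tables 8-3 and 16-5 (overall response).** Overall PR is "PR or CR in at least one organ with baseline involvement AND no progression in any other organ". Overall CR needs every organ to be in CR or not involved.
- **Prose definitions of overall response (Protocol 12.4.1 and 16.4.3, SAP 2.5.1).** PR is improvement in at least one organ without progression elsewhere and without new systemic therapy. Baseline involvement is not mentioned. CR is resolution of all signs and symptoms in all evaluable organs.
- **SAP 2.5.1.** The primary endpoint uses CR or PR "according to the NIH Consensus Criteria", as reported in the CRF, and refers back to Protocol Tables 8-3 and 16-3 for the remaining categories.

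**The concern.** Baseline involvement has two jobs in the overall-response tables. It decides whether an organ that has not reached CR blocks an overall CR, and it decides whether an organ's improvement can support an overall PR. With two definitions in one appendix, two sites can follow the protocol faithfully and record different overall responses from identical scores.

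The affected child is one with joint score 0 and P-ROM below 25 at Cycle 1 Day 1. At stake are the CR and PR counts reported as a supportive analysis and, on a narrower route, responder status. The same classification feeds ORR at Cycle 7 Day 1 and Cycle 4 Day 1, BOR, DOR and the corticosteroid-free response rate. The sensitivity analysis in SAP 2.5.4 excludes subjects whose response was not assessed by the protocol criteria (deviation OTH14). That deviation cannot be judged consistently for these children while there are two criteria.

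**Working it through.** **1. The two definitions.** P-ROM runs from 4 to 25 (measures list reproduced in Section 16.3), so 25 is full range.
- Text rule (16.4.2.3): involved if score is 1 or more.
- Table rule (Table 16-3): involved if score is 1 or more, or P-ROM is below 25. The table does not print the second half. It follows from CR being available after involvement by at least one measure, and from no involvement needing score 0 and P-ROM 25 together.

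The rules disagree only for score 0 with P-ROM below 25.

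**2. Cases, with all other organs unchanged unless stated.** The overall columns apply Tables 8-3 and 16-5.

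| Baseline | Post-baseline | Joint response | Overall, table rule | Overall, text rule |
|---|---|---|---|---|
| Score 0, P-ROM 24 | Score 0, P-ROM 25 | CR (Table 16-3); meets the PR bullets of 16.4.2.3 | Responder | Not a responder |
| Score 0, P-ROM 21 | Score 0, P-ROM 22 | PR | Responder | Not a responder |
| Score 0, P-ROM 24 | Unchanged; all other involved organs in CR | Unchanged | PR | CR |
| Score 1, P-ROM 21 (protocol's PR example) | Score 1, P-ROM 22 | PR | Responder | Responder |
| Score 1, elbow 6 (protocol's progression example) | Elbow 5 | Progression | Non-responder | Non-responder |

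Both worked examples in 16.4.2.3 start from score 1, where the rules agree, so they do not settle the conflict. Progression is unaffected, because any fall in P-ROM is progression under either rule.

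**3. How far the first two rows reach.** The joint label stays PR or CR under both rules. The non-response appears only when the text definition is used to read the baseline-involvement condition of Tables 8-3 and 16-5. Under the prose PR definitions both children are responders whichever definition of involvement applies. The third row does not depend on that step, because Tables 8-3 and 16-5 let a non-involved organ pass for overall CR. It leaves the child a responder either way.

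**4. Scale.** The plan's own figures reproduce from the exact binomial at a true ORR of 70%:
- n = 42: P(X ≥ 27) = 0.836; 27/42 has a 90% Clopper-Pearson interval of 0.505 to 0.765.
- n = 46: P(X ≥ 30) = 0.809; 30/46 gives 0.521 to 0.768.

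One subject fewer at those boundaries moves the lower limit from 0.521 to 0.499 (29/46), or from 0.505 to 0.480 (26/42).

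The documents give no frequency for score 0 with P-ROM below 25. Purely as assumptions, suppose 5% to 20% of children start in that state, 20% to 40% of those gain a P-ROM point, and joints decide the overall response in 10% to 30% of those. With the 46 enrolled:
- Low: 46 × 0.05 × 0.20 × 0.10 = 0.05 subjects (0.1 ORR points).
- High: 46 × 0.20 × 0.40 × 0.30 = 1.10 subjects (2.4 ORR points).

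None of the three inputs comes from the documents. The range shows only that the likely order is one subject or fewer. The FAS may be below 46, because SAP 2.2 moves some subjects to the listing-only set.

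**The case against.** The strongest reply is that the mismatch hardly touches the primary endpoint.

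- **The prose PR definitions rescue the joint-only responder.** This stands. A reader might infer that a P-ROM gain from 24 to 25 is unchanged disease under the text. It is not: the PR bullets of 16.4.2.3 carry no involvement condition, and the unchanged column of Table 16-5 needs every organ to be unchanged.
- **CR versus PR does not move the main endpoints.** This stands. ORR, BOR and DOR all count CR or PR, so only the supportive category breakdown is exposed on that route.
- **The affected group should be small on the protocol's own scoring.** This largely stands. Joint score 0 means no symptoms, and score 1 already covers mild tightness with normal or mildly reduced motion. A child restricted by cGvHD would usually score at least 1. Restriction from another cause is still scored, but flagged separately on the CRF (Section 8.3.1.2.1).
- **The appendix structure points to the text as the study-specific rule.** This stands only in part. Section 16.4.2 presents Table 16-3 as the criteria and the text as further detail and examples. The joint row's pointer to the text sits only in the cell for situations that are neither response nor progression. There is no precedence statement. The prose definition of CR, which requires all signs and symptoms to resolve, favours the table.
- **The boundary comparison is selective.** This stands. At a true ORR of 70%, exactly 29 of 46 has probability about 0.07, and 32/46 has a lower limit of 56.6%.

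**Conclusion.** The contradiction is certain. Its effect is probably very small. It definitely leaves CR versus PR open for a child with score 0 and P-ROM below 25 when all other involved organs have cleared. It leaves responder status open only where joints are the sole improved organ, nothing has progressed, and the text definition is carried into Tables 8-3 and 16-5.

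Two stronger conclusions are tempting and not supported. One is that the ORR result is unreliable or could fail a threshold. The 50% lower limit is a sample-size planning target, Protocol 12.7 and SAP 2.5.2 state that no hypothesis is tested, and the subject counts above rest on assumptions alone. The other is that the primary response should be re-derived. SAP 2.5.1 takes it from the CRF, and SAP 2.5 does not repeat that analysis for the final report unless data have changed. Replacing the source after the interim analysis, with a definition that can add responders, would be harder to defend than the ambiguity.

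A correction is still worth making. DOR, BOR to study end and the corticosteroid-free response rate are in the final report and use the same classification.

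**What to change.** 1. Change the involvement sentence in Protocol 16.4.2.3 to: *baseline involvement is an NIH Joint and Fascia score of 1 or more, or a P-ROM total below 25.* This matches Table 16-3 and the reproduced NIH table.
2. Keep the CRF-reported overall response as the source for the primary analysis.
3. Add to the SAP a listing or sensitivity analysis, from the joint scores and P-ROM values already collected, of subjects whose overall response differs under the two definitions. Cover Cycle 4 Day 1, Cycle 7 Day 1 and the later assessments used for BOR and DOR. Show the effect on the CR and PR counts and on responder status. An empty listing closes the question.

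The cost is one sentence and a small amount of programming. A subject or so may change category in the sensitivity analysis.
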